- Fasting insulin level, calculation of HOMA-IR and QUICKI indices (measures of insulin resistance; fasting insulin samples will be banked for assays to be performed in the future)
- hsCRP (samples will be banked for assays to be performed in the future), leukocyte counts (total WBC, absolute neutrophils and lymphocytes)
- Hypoglycemic symptoms (if any)
- Weight and BMI
- Any other side effects or changes in physical findings
- Compliance with all concurrent medications and study medications
- Diet and lifestyle adherence

Concurrent metformin and SU dosages will be maintained, unless down-titration of the sulfonylurea agent is necessary to prevent excessive hypoglycemia. Subjects will be advised to maintain the same dietary and activity routines throughout the course of the study.

Down-Titration of SU: In the event of new onset symptomatic hypoglycemia that is not attributable to dietary factors that are within the subject's control, the total daily dose of SU

should be reduced by 50%. If dietary factors that are within the subject's control are identified as precipitants to the hypoglycemia, then the subject should be counseled on reversing the dietary factors, and SU dose reduction may not be necessary. Interim assessments prior to the next scheduled visit (in 2 months) may be scheduled at the discretion of the investigators to assess the outcome of the counseling and/or dose reduction, and further reductions in the SU dosage may be made at the interim visits to alleviate the new onset symptomatic hypoglycemia. If the 50% dose reduction is insufficient to correct the hypoglycemia, then discontinuation of the SU may also be considered. No other changes to doses of SU will be permitted.

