Screening Visit (Week 0): Consent, screening, review of inclusion and exclusion criteria, and all required subject assessments for the study will take place at the CDU CTRC. A signed authorization for the release of medical records from MLK or SCFHC for the purposes of this study will be needed from all consented subjects to permit the investigators to review the relevant results when they become available. If all entry criteria are met, blood will be taken for the following laboratory tests: CBC, electrolytes, BUN, creatinine, FPG, HbA_{1c}, AST, ALT, fasting insulin, and hsCRP; urine will be collected for a urine pregnancy test (for women of childbearing potential). For subjects from MLK, all blood and urine samples with the exception of fasting insulin and hsCRP will be drawn by the MLK outpatient phlebotomists as per the diabetes clinic's routine treatment protocols, and the investigators will retrieve those results for review when they become available; fasting insulin and hsCRP blood samples will be obtained separately by phlebotomists at the CTRC. The above laboratory tests with the exception of fasting insulin and hsCRP are not required if they have already been performed by the laboratory within the previous 4 weeks and the results are accessible to the study team. For subjects from SCFHC, any of the above laboratory test results performed within the previous 4 weeks will be requested by the investigators, and any that were not performed within the previous 4 weeks will be drawn by the CTRC (including the fasting insulin and hsCRP).

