as with Week 0, all samples except fasting insulin and hsCRP will be obtained by the MLK phlebotomists and results will be reviewed when available; urine will be collected and processed by the MLK laboratory for a urine pregnancy test for women of childbearing potential at each follow-up visit; fasting insulin and hsCRP samples will be obtained separately at the CTRC. For subjects from SCFHC, all samples will be obtained at the CTRC (since the distance from SCFHC to CDU makes obtaining routine lab tests at SCFHC unrealistic when visits must take place at the CTRC). Based on current clinical evidence, diabetic patients are not required to perform self-glucose monitoring in the absence of insulin use, although subjects may perform self-glucose monitoring on their own if desired. Any hypoglycemic symptoms or any other adverse experiences will be reviewed and an attempt will be made to explain their occurrence. The subject's concurrent medications will be reviewed to ensure that dosages and compliance have not changed; any changes will be logged and subjects will be appropriately counseled. The entire study will last approximately 4 months.

Visit #	1	2	3
Week	0	8	16
Consent, inclusion / exclusion criteria	X		
Review of history / physical findings	X	X	X
CBC, Chemistry, FPG, HbA _{1c} , Urine pregnancy test ^a (obtained at MLK, SCFHC or CTRC)	X	X	X
Vitals, Weight, Height	X	X	X
Fasting insulin, calculation of HOMA-IR and QUICKI, hsCRP (obtained at CTRC, banked)	X	X	X
Randomization (if all criteria met)	X		
Dispense study medication supply	X	X	
Collect unused study medication supply; pill counts		X	X
Review of hypoglycemia	X	X	X
Review of adverse events		X	X
Reinforce nutrition / lifestyle	X	X	X
Review concurrent medications	X	X	X

^a For women of childbearing potential.

Assessment Measures (performed at CTRC):

- Vital signs, height and weight will be obtained at each visit, along with a brief review of the patient's history and physical findings at week 0 to look for exclusion criteria.
- Compliance with the subject's usual nutritional and lifestyle activities will be reviewed and reinforced.
- Changes in concurrent medications will be assessed at each encounter. Every effort will be made to avoid changes in concurrent medications that may influence carbohydrate or lipid metabolism (unless down-titration of SU is required).

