Laboratory Measurements: All laboratory analyses except fasting insulin and hsCRP will be obtained by the respective clinic phlebotomists specified above, and conducted by the respective clinical laboratories specified above, or the CTRC. Samples for insulin and hsCRP levels will be obtained at the CTRC, banked, and will be measured in the future by the CTRC Core Lab using commercially available RIA and/or ELISA kits: Millipore HI-14K Human Insulin RIA (Millipore, Billerica, MA); MP Biomedicals 07BC-1119 ultrasensitive CRP ELISA (MP Biochemicals, Orangeburg, NY); samples for insulin and hsCRP will remain frozen until assay reagents are available for batched runs once all samples have been collected.

Statistical Analyses:

All data will be collected onto Excel spreadsheets. Non-normal data will be log-transformed, as appropriate.

Intended Primary Endpoint: *The between-group change in the HbA_{1c} level from baseline to 4 months.*

Intended Secondary Endpoints:

A) The between-group difference in the change by 4 months of: i) % of subjects achieving HbA_{1c} $< 7.5\%$, ii) FPG, iii) weight and BMI, iv) HOMA-IR and QUICKI, and v) hsCRP and leukocyte counts;

B) For each group, the within-group change by 4 months in HbA_{1c}, FPG, weight and BMI, HOMA-IR and QUICKI, hsCRP, and leukocyte counts;

C) The between-group difference in the incidence of i) all hypoglycemic events, ii) severe hypoglycemic events, and iii) all adverse events excluding hypoglycemia.

Analysis: Changes in all continuous outcome measures will be compared between groups using 2-way repeated measures ANOVA. A chi-square analysis will be used to compare the percent of subjects achieving HbA_{1c} $< 7.5\%$ between groups. Changes within groups between baseline and

4-months will be made with one-way ANOVA. We will plan to eventually conduct both an intent-to-treat (ITT) analysis (missing data imputed using last-observation carried forward) as well as a secondary analysis of only those completed subjects with mean medication compliance $\geq 90\%$.

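### Baseline HOMA-IR and QUICKI may pair a Week 0 insulin with a glucose up to 4 weeks old, while the Week 8 and Week 16 indices have no such look-back

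*Combined protocol and SAP*

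**What the plan says.** The Screening Visit (Week 0) section of the protocol lists the baseline tests as "CBC, electrolytes, BUN, creatinine, FPG, HbA_{1c}, AST, ALT, fasting insulin, and hsCRP", so FPG and insulin both belong to Week 0. It then adds a waiver: the tests other than fasting insulin and hsCRP "are not required if they have already been performed by the laboratory within the previous 4 weeks" and the study team can access the results. Only insulin and hsCRP are exempt from reuse; FPG is not.

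The arrangements by clinic are:

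- **MLK, baseline.** Clinic phlebotomists draw the routine tests, and "fasting insulin and hsCRP blood samples will be obtained separately by phlebotomists at the CTRC".
- **SCFHC, baseline.** Results from the previous 4 weeks are requested from the clinic, and the CTRC draws only what is missing, plus insulin and hsCRP.
- **MLK, Weeks 8 and 16.** The routine tests are again taken by MLK, and "fasting insulin and hsCRP samples will be obtained separately at the CTRC".
- **SCFHC, Weeks 8 and 16.** Everything is drawn at the CTRC.

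Schedule of Procedures lists "Fasting insulin level, calculation of HOMA-IR and QUICKI indices" at every visit. Under Statistical Analyses, the 4-month change in both indices is a secondary endpoint between groups (A iv) and within each group (B).

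**The concern.** HOMA-IR and QUICKI are each computed from one fasting glucose and one fasting insulin, and are meant to describe a single fasting state. When the glucose was taken up to 4 weeks before the insulin, the result describes no single state. Because the look-back exists only at Week 0, the two ends of the change score are also constructed differently for the affected subjects. For SCFHC subjects with a reused result, the place where glucose is drawn changes as well, from the clinic at baseline to the CTRC at follow-up.

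These two indices are the protocol's only measures of insulin resistance. The background section says that a failure of insulin sensitivity to improve on HCQ would be read as evidence that inflammation does not contribute to insulin resistance. An endpoint carrying that interpretation, in at most 60 subjects, should not rest on an avoidable inconsistency in how it is measured.

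**Working it through.** **1. Does the text permit the mismatch?**

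| Visit | Glucose | Insulin | Look-back allowed? |
|---|---|---|---|
| Week 0 | Drawn, or reused from the previous 4 weeks | Always newly drawn, at the CTRC | Glucose yes, insulin no |
| Weeks 8 and 16 | Drawn for the visit | Drawn for the visit, at the CTRC | No |

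Schedule of Procedures and the visit table list FPG at every visit, but neither withdraws the waiver. Laboratory Measurements says "Samples for insulin and hsCRP levels will be obtained at the CTRC, banked" and does not ask for glucose on that draw. No section requires a same-day pair. The mismatch is therefore permitted at baseline.

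**2. How does glucose enter the indices?** The protocol does not print the formulas. The standard definitions are assumed:

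- HOMA-IR = glucose (mg/dL) × insulin (µU/mL) / 405
- QUICKI = 1 / (log10 glucose + log10 insulin)

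HOMA-IR is proportional to glucose: a value 10%, 20% or 30% higher raises it by 10%, 20% or 30%. QUICKI moves less. At an assumed insulin of 15 and glucose of 160, the same differences lower it by about 1.2%, 2.3% and 3.3%.

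**3. Does the mismatch add noise to the change score?** The earlier glucose replaces the same-day glucose; it is not added to it. Let sG and sI be the within-person SDs of log glucose and log insulin, and ρ their same-day correlation. Assume no drift and independence between occasions. For the change in log HOMA-IR:

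- Same-day pairs at both ends: variance = 2(sG² + sI²) + 4ρ·sG·sI
- Mismatched baseline, paired follow-up: variance = 2(sG² + sI²) + 2ρ·sG·sI

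The two differ by 2ρ·sG·sI, which takes the sign of ρ.

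Illustrative assumptions, none of them in the documents: FPG CV 15%, insulin CV 25%, and every subject with a reused glucose. With s = √ln(1 + CV²):

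- sG² = ln(1.0225) = 0.0223 and sI² = ln(1.0625) = 0.0606
- 2(sG² + sI²) = 0.1658
- sG·sI = 0.1492 × 0.2462 = 0.0367

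| ρ | Same-day variance | SD | Mismatched variance | SD |
|---|---|---|---|---|
| −0.3 | 0.1658 − 0.0441 = 0.1217 | 0.349 | 0.1658 − 0.0220 = 0.1437 | 0.379 |
| 0 | 0.1658 | 0.407 | 0.1658 | 0.407 |
| +0.3 | 0.1658 + 0.0441 = 0.2098 | 0.458 | 0.1658 + 0.0220 = 0.1878 | 0.433 |

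The SD is about 9% higher (0.379/0.349), unchanged, or about 5% lower (0.433/0.458). If only a fraction of subjects reuse a result, the average change in variance shrinks in proportion.

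**4. What of drift?** If a subject's usual glucose moves between the earlier draw and Week 0, the mean movement shifts the baseline index and its spread adds variance. The documents give neither figure.

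**The case against.** The strongest reply is that same-draw pairing is better practice but that no harm has been shown. Most of this stands.

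- **Bias.** A reader might infer that the older FPG runs high because it precedes study counselling, so that HOMA-IR would seem to fall in both arms. The documents do not support this. The Week 0 sample also precedes any effect of study counselling, subjects are told to keep their usual diet and activity, and entry requires at least 3 months on maximum tolerated metformin and a sulfonylurea. If the reused FPG also served the exclusion at 300 mg/dL, regression to the mean would make it read low, the opposite direction. The waiver is worded alike for both arms and precedes treatment, so it gives no reason to expect a biased between-group contrast.
- **Noise.** A reader might take the spread between two FPG values, √2 times the within-person CV, as extra error and convert it into lost power. That double-counts: a same-day FPG carries the same day-to-day variation, and any two visits in a perfectly paired design differ by as much.
- **MLK follow-up.** A reader might count the separate MLK and CTRC draws at Weeks 8 and 16 as a second mismatch. Separate draws are not shown to be on different days. The follow-up section describes one fasting visit with both tests listed.
- **Scale.** Drawing FPG at Week 0 is the default, the share of reused results is unknown, and these are secondary endpoints of a pilot limited by funding.

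None of this removes the waiver, or makes a mixed-date baseline index comparable in construction with the later ones.

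**Conclusion.** The point holds in a limited form. The screening rules allow a baseline HOMA-IR and QUICKI that come from no single fasting state and are constructed differently from the Week 8 and Week 16 values. This weakens the interpretation of secondary endpoints A iv and B, the within-group change more than the between-group one.

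The documents do not establish a direction of bias, a loss of power, or even that the noise increases. That depends on the within-person glucose–insulin correlation, on drift over the gap, and on the share of subjects with a reused result, none of which they give. The SDs shown illustrate that the sign is open; they do not estimate an effect. The HbA1c endpoint does not use these indices. Severity is minor: a cheap improvement in measurement.

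**What to change.** 1. For endpoint purposes, add FPG to the tests excluded from the 4-week waiver. Reused results may still serve eligibility.
2. Measure glucose on the same fasting CTRC draw as insulin at Weeks 0, 8 and 16 in every subject, and state under Statistical Analyses that HOMA-IR and QUICKI are computed only from those pairs.
3. For subjects already sampled, record the dates of both draws, report how many baselines used an earlier FPG, and run a sensitivity analysis restricted to same-day pairs.

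**Cost.** At most 60 subjects × 3 visits = 180 extra glucose assays, and fewer in practice because the CTRC already draws FPG for SCFHC subjects at follow-up. The blood is already being taken, so no visit or needle stick is added. Step 3 needs only the dates and one additional analysis, at the price of a smaller subset if reuse proves common.

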Secondary Outcomes: To collect preliminary data to eventually compare a) the percentage of patients who achieve HbA_{1c} <7.5% after receiving either HCQ or PIO for 4 months; b) the effect of PIO vs. HCQ in lowering fasting plasma glucose (FPG) and weight; and c) the effects of HCQ vs. PIO on inflammation and insulin resistance.

Research Design: A 4-month, randomized, prospective, open-label comparison trial

Subjects: Type 2 diabetic patients inadequately controlled on maximally tolerated doses of metformin plus a SU.

Recruitment: Subjects will be recruited from the Diabetes Programs at MLK and South Central Family Health Center (SCFHC). These centers serve the same large population of low-socioeconomic status and low-educational level ethnic minority patients living in the south and south-central region of Los Angeles. The diabetes clinic at MLK is staffed by the faculty of the Endocrinology Division of Charles R. Drew University of Medicine and Science, and the diabetes care providers at the SCFHC clinic were trained on the same treatment protocols by the study co-investigator. This study protocol will be reviewed by the Institutional Review Board of Charles R. Drew University prior to study initiation, and an IND application will be submitted to the FDA.

Inclusion Criteria:

- Male or female, age 18-75, inclusive
- Known type 2 diabetes (diagnosed according to 1997 ADA diagnostic criteria) receiving diabetes treatment at MLK or SCFHC
- At least 3 months of treatment with maximum tolerated doses of metformin *and* a SU, *and* inadequate glycemic control (HbA_{1c} ≥ 7.5% and < 11.0%)
- Body mass index (BMI) < 45 kg/m²
- Able to comply with all scheduled visits and requirements of the protocol

Exclusion Criteria:

- Any contraindications to the use of metformin or a SU
- Extreme hyperglycemia (FPG ≥ 300 mg/dL), symptoms of polyuria or polydipsia, or HbA_{1c} ≥ 11.0%
- Current use of insulin; history or clinical suspicion of type 1 diabetes mellitus
- Symptomatic hypoglycemia occurring at an average frequency > once per day
- Highly erratic dietary schedules, extremely food insecure households, or homelessness that may adversely affect good glycemic control, as judged by the investigators
- Occupations that involve regular operation of motor vehicles or other heavy machinery that may pose a hazard in the event of unanticipated blurred vision

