- Known history of Class III or IV heart failure, cardiac arrhythmias, severe peripheral edema, advanced osteoporosis, documented bladder malignancies, or other intolerance to PIO
- Known history of collagen vascular disorders, glucose-6-phosphate dehydrogenase deficiency, hematologic disorders, psoriasis, or any known intolerance to HCQ

- Known history of pre-proliferative or proliferative retinopathy, or any clinically significant retinal abnormalities noted on the patient's most recent (i.e., within 1 year) ophthalmologic exam; subjects who have not received their routine annual ophthalmologic surveillance for diabetic retinopathy within the past year must have their annual surveillance performed before screening
- An estimated GFR (by the Modification of Diet in Renal Disease (MDRD) formula) < 45 mL/min, or a history of nephrotic syndrome (defined as a spot urine protein-creatinine ratio of > 3500 mg per g urine creatinine)
- Subjects with active hemoglobin abnormalities that render the HbA_{1c} measurement unreliable
- History of any clinically significant hepatic, cardiovascular, infectious, dermatologic, psychiatric, or other major systemic disease that, in the opinion of the investigator, may make the use of PIO or HCQ unsafe, or otherwise make the interpretation of the data difficult.
- Female subjects of childbearing potential who are sexually active and not using a reliable form of contraception or do not agree to use a reliable form of contraception. Reliable forms of contraception include systemic contraceptives (oral, implant or injection), diaphragm with spermicide, cervical cap, IUD, or condoms with spermicide.
- Current pregnancy or lactation.
- Subjects who will likely require or initiate therapy with drugs that may interfere with glucose metabolism during the course of the study (e.g., glucocorticoids).
- Subjects who are in another investigational study or have received another investigational medication within 30 days of study entry
- Subjects who are unable or unwilling to give informed consent, comply with all components of the study protocol, attend all scheduled follow-up visits, or present other barriers that would make the implementation of the protocol unusually difficult.

Schedule of Procedures: This study will be approximately 4 months in duration. Subjects will be assessed at baseline, 2 and 4 months. All visits will include an assessment of:

- Fasting plasma glucose (FPG)
- HbA_{1c}

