Study Medication: Subjects who satisfy all inclusion and exclusion criteria will be randomized to either PIO 45 mg once daily or HCQ 400 mg once daily (2 x 200 mg tablets). Randomization will occur based on the subject's (randomly assigned) unique medical record number issued by MLK or SCFHC: *odd numbers will receive HCQ; even numbers will receive PIO.* The study is open-label. The supply of PIO will be prescribed as per usual clinical practice through the outpatient pharmacies at MLK and SCFHC (or provided by the investigators if not obtainable from SCFHC because of their internal insurance coverage policies), and compliance will be determined by pill counts and referencing dispensing records from the MLK online pharmacy database (for subjects from MLK). The supply of HCQ will be purchased from a retail pharmacy specifically for the study, and compliance will be determined by pill counts assessed by the study coordinators at each follow-up visit. Subjects will be provided with a 90-day supply at the randomization visit so as to allow for potential variations in compliance and/or scheduling of the 2-month follow-up visit. Subjects must bring their remaining supply of unused medication at the every follow-up visit, and will be provided with a sufficient amount of additional HCQ at the 2-month visit to last until their final, 4-month visit (allowing again for potential variations in compliance and/or scheduling). Although all subjects should already have experience with the principles of dietary and lifestyle modifications as part of their ongoing diabetes therapy, these concepts will be reinforced at each follow-up visit.

Follow-Up Visits (Week 8, Week 16): Subjects will be seen at the CTRC in the fasting state, vital signs, weight and height will be taken, and blood will be drawn for FPG, HbA_{1c}, CBC, electrolytes, BUN, creatinine, AST, ALT, fasting insulin, and hsCRP. For subjects from MLK,

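### Allocation by odd or even medical record number is not concealed, so the arm can be known before entry and selection bias can reach the primary HbA1c comparison

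*Combined protocol and SAP*

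**What the plan says.** The Research Design section describes "A 4-month, randomized, prospective, open-label comparison trial". The Study Medication section gives the allocation rule: "odd numbers will receive HCQ; even numbers will receive PIO". The number used is the subject's "randomly assigned) unique medical record number issued by MLK or SCFHC", so it comes from the clinic and not from the trial.

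Five other parts of the protocol bear on how the rule works:

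- **Who is eligible.** Under Inclusion Criteria, candidates must be "receiving diabetes treatment at MLK or SCFHC". They hold their number before the trial reaches them.
- **Who is near the patients.** Recruitment states: "The diabetes clinic at MLK is staffed by the faculty of the Endocrinology Division" of the investigating university. SCFHC providers were trained by the study co-investigator.
- **Room for judgement.** One exclusion covers erratic diet, food insecurity or "homelessness that may adversely affect good glycemic control, as judged by the investigators". Another covers major disease that, "in the opinion of the investigator, may make the use of PIO or HCQ unsafe". A third refers to unspecified barriers to carrying out the protocol.
- **Timing.** The visit table puts consent, eligibility review and randomization at the same Week 0 visit, with randomization conditional on the criteria being met. Under Screening Visit (Week 0), "A signed authorization for the release of medical records from MLK or SCFHC" is required from consented subjects.
- **Analysis.** The intended primary endpoint is the between-group change in HbA1c from baseline to 4 months. It is compared by 2-way repeated measures ANOVA, with an intent-to-treat analysis planned.

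No section mentions sealed envelopes, central or pharmacy allocation, or masking of the number from those who recruit.

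**The concern.** Randomization gives two separate protections: a sequence unrelated to prognosis, and concealment of the next assignment until the patient is irrevocably in. The statement that record numbers are randomly assigned speaks to the first only. The second is absent. Under a published parity rule, a person who sees the number knows the arm with certainty; under concealed simple 1:1 randomization that person could only guess, with probability 0.5.

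The arms are also not equivalent in the eyes of staff and patients. The Background section says pioglitazone is the clinics' routine third drug, whereas hydroxychloroquine is bought specially for the study. Willingness to approach or to consent could therefore depend on the arm.

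If entry depends on the arm, the groups can differ before treatment begins. Both planned analyses cover only patients who were admitted, so they inherit that difference. More patients would shrink random error but not this bias. That matters because the Sample Size Calculations section hopes to continue the study to its full enrollment target, with non-inferiority as the eventual question.

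**Working it through.** The documents give no figure to reproduce: up to 60 subjects is a funding limit, and no SD, margin or effect size is stated. The check has a textual part and an illustrative part.

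**Text.** The rule is deterministic and depends only on a number issued before the trial. Listing randomization after eligibility in the visit table therefore hides nothing, because the result can be read beforehand. Where trial staff first get the number with the records release, that comes after consent, but the number can still be known while eligibility is judged at the same visit.

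**Bias in the endpoint (all inputs assumed).** Half of candidates are poor responders, whose 4-month HbA1c change is worse by D points. A fraction f of them is passed over in one arm only. Their share in that arm becomes p = 0.5(1 − f)/(1 − 0.5f), and the bias in the between-group change is (0.5 − p) × D.

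| f | p | D = 0.5 | D = 1.0 | D = 1.5 |
|---|---|---|---|---|
| 0.2 | 0.40/0.90 = 0.444 | 0.028 | 0.056 | 0.083 |
| 0.3 | 0.35/0.85 = 0.412 | 0.044 | 0.088 | 0.132 |
| 0.5 | 0.25/0.75 = 0.333 | 0.083 | 0.167 | 0.250 |

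For scale, with 30 per arm and an assumed SD of change of 1.0 to 1.5, the 95% half-width is 2.002 × SD × √(2/30) = 0.52 to 0.78 points. At SD 1.0 the standard error is √(2/30) = 0.258, so the largest bias in the table is 0.250/0.258 = 0.97 standard errors.

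**Would a baseline table reveal it?** Suppose instead that the fraction f of patients with above-median HbA1c is passed over in one arm. Assume a normal distribution truncated to the entry range 7.5 to 11.0, with mean 9.1 and SD 0.87 after truncation (assumed, not from the documents). The means above and below the median then differ by 1.457 points, and the shift in mean baseline HbA1c is (0.5 − p) × 1.457. Power is for a two-sided 5% t-test with 30 per arm.

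| f | Baseline shift | Power to detect it |
|---|---|---|
| 0.2 | 0.08 | 6.5% |
| 0.3 | 0.13 | 8.7% |
| 0.5 | 0.24 | 18.6% |

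If 0.87 is read as the SD before truncation, the shifts are 0.07, 0.11 and 0.21. These are shifts in a baseline variable, not endpoint bias. They show that similar-looking baseline means would be weak reassurance.

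**Arm sizes are not the issue.** If parity acts as a fair coin, a split of 36:24 or worse has probability 15.5%, and it raises the standard error only by √[(1/36 + 1/24)/(2/30)] = 1.02.

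**The case against.** The best defence is the stated aim. This is a pilot that collects preliminary data; it admits that it cannot reach its intended power, states no margin, and leaves any continuation to future funding. The illustrated bias rests wholly on assumed inputs, lies below the 60-patient half-width, and reaches 0.25 only if half of all poor responders are skipped in one arm and none in the other. That all stands. It limits how much harm can be claimed at pilot scale, but it does not supply concealment.

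The room for selection is also narrower than it may seem. Many criteria are objective (HbA1c, FPG, BMI, eGFR, insulin use, retinopathy), and the safety criterion applies to both drugs whichever arm is due. HbA1c is a laboratory value, which limits biased assessment. These points are fair, but discretionary exclusions remain, the decision to approach is unregulated, and an objective outcome does not protect against selective entry.

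Finally, the documents do not say who approaches patients or that anyone looks at parity, and the records release after consent applies to both clinics. University staffing of the MLK clinic does not by itself show that those staff recruit. So the protocol shows an open route for bias, not bias that occurred. Clinic staff nevertheless hold the numbers from the outset, and nothing in the protocol closes the route.

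**Conclusion.** The concern holds. The trial is called randomized, but its allocation is fully predictable to anyone who sees the record number, and no concealment is described. Selection bias can therefore enter the primary comparison, and the planned analyses cannot remove it. Its actual size and direction cannot be derived from the documents. Under the stated assumptions it is 0.03 to 0.25 HbA1c points, and a baseline comparison would probably miss selection of that strength. Whether parity is truly unrelated to prognosis cannot be checked either, but the conclusion does not depend on it. This must be fixed despite the pilot label: the remedy is cheap, and the flaw would carry into any continuation that keeps these patients.

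**What to change.** For every patient not yet allocated:

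- Replace the parity rule with a computer-generated 1:1 permuted-block list, preferably stratified by clinic. Vary the block sizes and keep them undisclosed, because in an open-label trial a known fixed block size lets staff predict later assignments.
- Have the list held by someone outside recruitment, or use sequentially numbered, opaque, sealed envelopes.
- Reveal the arm only after consent is signed and eligibility is confirmed and logged.
- Keep a log of patients approached, refused and excluded, with reasons. For the parity period, add the parity of the number.

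Describe patients already allocated by parity as quasi-randomized, and show results by allocation method as a sensitivity analysis. The documents do not give enrollment status. If allocation is complete, that label and any retrievable counts by parity are what remain, and concealed allocation applies to any continuation.

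The cost is one protocol amendment, a list or envelopes, and a short log, with no extra patients, visits or tests. The drawback of a mid-trial switch is imprecision by method. With 30 of 60 patients per method (15 per arm) and an assumed SD of change of 1.0 to 1.5, the 95% half-width is 2.048 × SD × √(2/15) = 0.75 to 1.12 points, so that sensitivity analysis could show only large discrepancies.
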